7.2 PARTICIPANT DISCONTINUATION/WITHDRAWAL FROM THE STUDY

Participants are free to withdraw from participation in the study at any time upon request. An investigator may discontinue or withdraw a participant from the study for the following reasons:

- Severe hyperglycemia or ketoacidosis during the study
- Adhesive allergy/intolerance developed during the study
- Any condition or change in condition compromising the safety of the participant as judged by the PI or someone in the team
- Pregnancy.
- Significant study intervention non-compliance.
- If any clinical adverse event (AE), laboratory abnormality, or other medical condition or situation occurs such that continued participation in the study would not be in the best interest of the participant.
- If the participant meets an exclusion criterion (either newly developed or not previously recognized) that precludes further study participation.
- Study participant unable to participate in the second series of glucose clamp experiments after 2 ± 1 week wash-out period.
- DKA, characterized by hyperglycemia with ketosis (serum ketones elevated to >1.5 mmol/L) and metabolic acidosis with depressed serum bicarbonate level to less than 18 mmol/L and/or arterial pH less than 7.30.

The reason for participant discontinuation or withdrawal from the study will be recorded on the CRF. Participants who sign the informed consent form and are randomized but do not receive the study intervention (placement of the first CSII catheter) may be replaced. Participants who sign the informed consent form, and are randomized and receive the study intervention, and subsequently withdraw, or are withdrawn or discontinued from the study, will not be replaced.

7.3 LOST TO FOLLOW-UP

A participant will be considered lost to follow-up if he or she fails to return for one scheduled visit and is unable to be contacted by the study site staff.

The following actions must be taken if a participant fails to return to the clinic for a required study visit:

- The site will attempt to contact the participant and reschedule the missed visit within a day and counsel the participant on the importance of maintaining the assigned visit schedule and ascertain if the participant wishes to and/or should continue in the study. Instructions shall be provided to the participant on returning to the site for EOS assessments and product return, if the participant decides to withdraw from the study.
- Before a participant is deemed lost to follow-up, the investigator or designee will make every effort to regain contact with the participant (where possible, 3 telephone calls and, if necessary, a certified letter to the participant's last known mailing address or local equivalent methods). These contact attempts should be documented in the participant's medical record or study file.
- Should the participant continue to be unreachable, he or she will be considered to have withdrawn from the study with a primary reason of lost to follow-up.

8 STUDY ASSESSMENTS AND PROCEDURES

8.1 EFFICACY ASSESSMENTS

Multiple samples will be taken during each clamp procedure and plasma insulin levels will be analyzed using insulin assays.

8.2 SAFETY AND OTHER ASSESSMENTS

The following labs and procedures will be conducted to ensure patient safety:

- **Physical examination** (e.g., height and weight, organ systems, motor or vision assessment, or other functional abilities). If appropriate, discuss what constitutes a targeted physical examination.
- **Vital signs** (e.g., temperature, pulse, respirations, blood pressure while seated). Carefully consider which vital signs (if any) should be measured to ensure that only essential data are collected. Include any specific instructions with respect to the collection and interpretation of vital signs.

- **Biological specimen collection and laboratory evaluations.** Urine pregnancy test, CBC to exclude anemic conditions, C-Peptide tests to confirm T1 diabetes and rule out T2 diabetes, and HbA1c levels at screening. Electrocardiogram to evaluate cardiac status. Frequent BG measurements to titrate D20% IV administration rate and keep patients in euglycemia range.
- **Special assays or procedures required.** Multiple plasma samples will be frozen and stored to measure insulin levels via radioimmunoassay (RIA)
- **Counseling procedures, including any dietary or activity considerations:** Patients will be trained on study procedures and will be asked to maintain their usual diet and exercise regimens during the course of the entire study. Prior to clamp visits, however, they are asked to refrain from strenuous exercise and eating meals high in carbohydrates.
- **Assessment of study intervention adherence:** a CGM device will be applied to identify any hyperglycemia or hypoglycemia.
- **Administration of questionnaires or other instruments** will be utilized to collect pain scores (VAS) and maintain AE records (phone visit and diary during washout period). Additionally, usability questionnaires will collect patient and clinician perspective on product usability to identify sources of user error.
- **Assessment of adverse events.** Reported AEs and SAEs will be reviewed by the investigator or designee and Medical Monitor.

8.3 ADVERSE EVENTS

8.3.1 DEFINITION OF ADVERSE EVENTS

An Adverse Event (AE) is defined any untoward medical occurrence associated with the use of an intervention in humans, whether or not considered intervention-related (21 CFR 312.32 (a)).

Investigational device adverse events/effects shall be reported as anticipated or unanticipated per CFR 812.3, and drug reactions and/or adverse drug effects shall be reported as described in CFR 312.32. Events shall be reported to the Sponsor per protocol and to the governing IRB per IRB requirements and all applicable study regulations.

A list of anticipated (expected) adverse effects related to the study device, study intervention or testing procedures and known complications of diabetes disease, insulin use, treatments and treatment equipment have been provided in reference document 150-1004-02 Feasibility Study Anticipated Adverse Event Definitions.

8.3.2 SERIOUS ADVERSE EVENTS AND UNANTICIPATED ADVERSE DEVICE EFFECTS

A Serious Life-threatening Adverse Event or Life-threatening Suspected Adverse Reaction is defined as an adverse event/effect or suspected effect that is considered “life-threatening” that if, in the view of either the investigator or sponsor, its occurrence places the patient or participant at immediate risk of death.

Serious adverse event (SAE)

A serious adverse event or serious suspected adverse reaction - defined as an adverse event or suspected adverse reaction is considered "serious" if, in the view of either the investigator or sponsor, it results in any of the following outcomes:

- death,
- a life-threatening adverse event,
- inpatient hospitalization or prolongation of existing hospitalization,
- a persistent or significant incapacity or substantial disruption of the ability to conduct normal life functions,
- or a congenital anomaly/birth defect.

A suspected adverse reaction means any adverse event for which there is a reasonable possibility that the drug caused the adverse event. Per federal regulations "reasonable possibility" means there is evidence to suggest a causal relationship between the drug and the adverse event.

Unexpected Adverse Event or Unexpected Suspected Adverse Reaction

An unexpected adverse event/effect is defined as an adverse event or suspected adverse reaction is considered "unexpected" if it is not listed in the investigator brochure or is not listed at the specificity or severity that has been observed; or, if an investigator brochure is not required or available, is not consistent with the risk information described in the general investigational plan or elsewhere in the current application, as amended.

Unanticipated Adverse Device Effects (UADE)

An unanticipated adverse device effect is defined as "any serious adverse effect on health or safety or any life-threatening problem or death caused by, or associated with, a device, if that effect, problem, or death was not previously identified in nature, severity, or degree of incidence in the investigational plan or application (including a supplementary plan or application), or any other unanticipated serious problem associated with a device that relates to the rights, safety, or welfare of participants."

For consideration of device safety and performance, an unanticipated adverse event is an event that has not been described in the investigational plan, study protocol, attachments, Instructions for Use, product labeling, or other product descriptions including those of ancillary study products.

A UADE must be directly related to the device under investigation.

The Sponsor is responsible for promptly reviewing any and all information relevant to the device or drug product and considering the impact of the all adverse event (s) on study continuation.

8.3.3 ADVERSE EVENT/EFFECT CLASSIFICATION

All adverse events shall be classified based on their relationship to the investigational device, intervention or test period; underlying disease state, pre-existing co-morbidity or concomitant therapy as described below:

Related – Anticipated AE known to occur with the study intervention, there is a reasonable possibility that the study intervention caused the AE, or there is a temporal relationship between the study intervention and event. Reasonable possibility means that there is evidence to suggest a causal relationship between the study intervention and the AE.

Unrelated – Definite assessment that there is no reasonable possibility that the study intervention caused the event, and no defined temporal relationship between the study intervention and adverse event onset, or an alternate etiology has been established.

Unknown - A determination of relationship to the product, test procedure or co-morbidity cannot be established.

Not Assessable - There is insufficient data to determine a relationship to the investigational product, procedure or other condition.

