2.3 RISK/BENEFIT ASSESSMENT

2.3.1 POTENTIAL RISKS

A list of known disease, treatment, CSII sets, glucose pump and CGM product risks and potential risks are listed below. A list of anticipated adverse events and study definitions can be found in Section 8.3 of this protocol. There may be other risks that are unknown at this time and new risks that may be identified during the study.

Fingerstick

- Fingerstick BG tests may produce pain and/or bruising at the test site.

Diabetes Disease Risks

- Hypoglycemia and associated symptoms such as sweating, trembling, difficulty thinking and dizziness
- Hyperglycemia
- Diabetic ketoacidosis
- Coma
- Death

Insulin pump Use/Therapy

- Slight bruising at the site of insertion (common)
- Slight discomfort at the time of insertion of the insulin delivery cannula (common)
- Bleeding at insertion site (rare)

- Clinically significant infection or inflammation at the site of insertion (very rare), due to the extended cannula wear time this risk might be slightly higher but is considered to occur only rarely.
- Allergy to insulin (very rare)

Note: Participants will be instructed to regularly check the insertion site for any skin reactions. Skin reactions shall be noted in the provided diary and the study team shall be contacted via the helpline.

Commercial CSII Catheter Insertion Site Reactions

- Reddening
- Induration
- Purulence
- Itching
- Other non-specified skin irritation

Venipuncture and IV catheter insertion

- Localized infection – an infection in the tissue around the site
- Phlebitis – inflammation of the wall of the vein
- Hematoma – an accumulation of blood within the tissues that clots to form a solid swelling
- Fatigue caused by transient anemia due to frequent blood draws (insulin and glucose concentration determination)
- Thrombus formation and necessary insertion of a new IV catheter

Continuous Glucose Monitoring Risks

- Trivial discomfort at the time of insertion of CGM (common)
- Slight bruising at the site of insertion (unlikely)
- Bleeding at insertion site (rare)
- Infection at the site of insertion (rare)

Humalog (insulin lispro injection, USP [rDNA origin]) for injection (ID: 3273563)

- Allergy
- Anaphylaxis
- Antibody Production
- Hypokalemia
- Lipodystrophy
- Peripheral Edema
- Renal or Hepatic Impairment
- Weight gain

Glucose Clamp Related Risks

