9.4.4 SAFETY ANALYSES

Tolerability of infusion sets will be assessed by comparing the mean VAS scores from day of insertion through Day 7 of use with a mixed-effects (repeated-measures) linear model with treatment, period and day as fixed effects and participant as a random effect. The mean difference between treatments will be compared with a two-sided test using significance level $\alpha=0.05$.

Adverse events (AEs) will be coded using CTCAE v4.0. Descriptive statistics (number of participants and per-participant incidence) for device-related AEs will be presented by System Organ Class, Preferred term, severity and treatment. Unanticipated and serious device-related AEs will be presented separately by treatment.

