4.4.5 Safety Analysis

4.4.5.1 Adverse Events

Adverse events will be listed only if the total # of AE in the whole study is less than 5.

Otherwise, they will be summarized by presenting, for each dose/treatment group, the number and percentage of participants experiencing any adverse event, experiencing an adverse event in each system organ class (SOC) and experiencing each individual adverse event.

- If two events of the same symptom of the same subject happens within 5 minutes, it will be considered as a single event in the summary.

Subgroups of intensity and subgroups of device-related tables should also be presented.

Any other information collected (e.g. severity or relatedness to study medication) will be listed as appropriate.

Population	Safety
------------	--------

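### The adverse-event relatedness categories overlap: an event during wear with another established cause can be both Related and Unrelated, and no rule says how either call feeds the device-related tables

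*Protocol*

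**What the plan says.** Protocol 8.3.3 opens by saying events are "classified based on their relationship to the investigational device, intervention or test period", and it adds disease, co-morbidity and concomitant therapy. It then defines four categories.

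- **Related** has three limbs joined by *or*. The first is "Anticipated AE known to occur with the study intervention". The second, in substance, is that causation is reasonably possible. The third needs only timing: "or there is a temporal relationship between the study intervention and event".
- **Unrelated** requires no reasonable possibility of causation and no defined temporal relationship, and then adds "or an alternate etiology has been established".
- **Unknown** and **Not Assessable** cover events whose relationship cannot be determined. Unlike the first two, they name product and procedure separately.

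Protocol 6.1.1.8 explains the study intervention as insulin infusion through the CSII catheter; protocol 7.2 explains it as placement of the first catheter. Among the data required for each event, protocol 8.3.5 names one relationship item, to the study product.

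On reporting, protocol 9.4.4 says descriptive statistics "for device-related AEs will be presented by System Organ Class, Preferred term, severity and treatment". SAP 4.4.5.1 summarises all events by treatment, system organ class and individual event, and adds: "Subgroups of intensity and subgroups of device-related tables should also be presented". The same SAP section later speaks of relatedness to study medication.

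**The concern.** A relatedness rule has to give one answer per event. This one can give two, for a kind of event the design makes likely. Each wear period contains up to four clamps, each with IV lines in place while the study set is worn, and a CGM sensor is worn alongside. Protocol 2.3.1 lists the risks of those procedures under their own headings; under venipuncture and IV catheters, for example, it lists "Thrombus formation and necessary insertion of a new IV catheter". Such an event coincides in time with the study intervention and has a known other cause.

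Where both definitions fit, the investigator chooses, and protocol 4.1 describes the trial as open. What is at stake is the meaning of the device-related tables. Without a rule leading from the 8.3.3 category to the label device-related, a reader cannot tell whether a count reflects the infusion set alone or also the procedures around it.

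**Working it through.** No figure in the plan needs reproducing. The check is logical.

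**Inputs, all from protocol 8.3.3.** Each condition is either true or false for an event:
- K: anticipated and known to occur with the intervention
- P: reasonable possibility of causation
- T: temporal relationship
- E: alternate etiology established

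Four conditions give 2^4 = 16 combinations.

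**Definitions.** Related = K or P or T. The *and ... or* in Unrelated can be read in two ways:
- Reading 1: (not P and not T) or E
- Reading 2: not P and (not T or E)

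**Overlap as written.**
- Reading 1: with E true, every combination of K, P and T except all-false is also Related, which gives 8 - 1 = 7. With E false, only K true, P false, T false meets both, which gives 1. Total: 7 + 1 = 8 of 16.
- Reading 2: P must be false. T false with K true gives 2 (E either way); T true with E true gives 2 (K either way). Total: 2 + 2 = 4 of 16.

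The case at issue (T and E true, K and P false) meets both definitions under either reading. No combination falls outside both. These are counts of logical cases, not expected proportions of events.

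**Which repair works.**

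| Change to Related, Unrelated left as is | Overlap, reading 1 | Overlap, reading 2 |
|---|---|---|
| Drop T only (K or P) | 7 of 16 | 3 of 16 |
| P only | 4 of 16 | 0 of 16 |
| P and not E | 0 of 16 | 0 of 16 |

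Deleting the temporal limb is therefore not enough. The last row removes the overlap but leaves gaps if Unrelated is not reworded. Events with P false, T true and E false then fit neither definition (2 combinations, K either way). Under reading 2, so do events with P and E both true (4 more, making 6). Unrelated must therefore be rewritten as the complement.

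**From category to table.** The text moves between several objects:
- device, intervention or test period (8.3.3 lead-in)
- study intervention (Related and Unrelated)
- study product (8.3.5)
- device (9.4.4 and SAP 4.4.5.1)
- study medication (SAP 4.4.5.1)

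No sentence in either document links an 8.3.3 category to the device-related label, and no separate attribution to clamp, IV line or CGM is described.

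**The case against.** A reader might infer that the device-related tables will in fact contain every event with onset during wear. The documents do not support that, for these reasons:

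- No rule equates Related with device-related. An analyst could work from the product-relationship item in 8.3.5.
- The 8.3.3 lead-in, the Unknown and Not Assessable definitions, and the headings in 2.3.1 all distinguish device from procedure.
- An IV-site event can be coded Unrelated under the same text.
- Reading mere coincidence over seven days as a temporal relationship is the widest available reading.
- The case report forms and the anticipated-event list cited in 8.3.1 are not available here, so separate attribution may exist there.

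The consequence is also limited. Infusion-site infection or inflammation, dislodgement and other malfunctions are counted separately from the relatedness call (SAP 4.3.3.1.3 to 4.3.3.1.5 and 4.4.5.4). The event tables are split by organ class and event, so phlebitis would not share a row with infusion-site erythema. SAP 4.4.5.1 includes an all-event summary. Non-serious hypoglycemia is not reported as an adverse event (protocol 8.3.8). The study stopped after the seventh completer (SAP 2.5), and with fewer than five events there are only listings.

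A second tempting inference is that the longer-surviving set must look worse because it undergoes more clamps. Exposure can differ: note 6 to the Schedule of Activities omits the clamp once a failed cannula has been removed. But the documents give no rate of procedure events per clamp and no basis for comparing wear by set. Unequal exposure would affect the all-event table as well, and both periods plan the same procedures.

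All of this limits the consequence. None of it removes the overlap or supplies a tie-break.

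**Conclusion.** The rule is faulty as written. Temporal association alone makes an event Related, an established other cause can make the same event Unrelated, and nothing decides between them. This holds under both readings of the Unrelated definition (8 or 4 of 16 logical combinations). It assumes only that the limbs of Related are alternatives, as the *or* indicates.

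The effect on the device-related tables is a possibility: they may absorb clamp, IV or CGM events. Neither the number of events nor the direction of any distortion between sets can be derived from the documents. With so few completers, one or two misattributed events could alter a device-related count, whether it appears in a table or a listing.

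**What to change.** 1. **Make the categories mutually exclusive.** Define Related to the infusion set as a reasonable possibility that the set caused the event. Temporal association supports that judgement but does not suffice, and an established alternate etiology excludes it. Reword Unrelated as the complement, leaving Unknown and Not Assessable for events where the question cannot be answered.
2. **Separate the attributions.** For both Achilles and control, record relatedness to (a) the infusion set, (b) the clamp or IV procedure, (c) CGM, and (d) insulin or underlying disease.
3. **Define device-related.** State in protocol 9.4.4 and SAP 4.4.5.1 that it means attribution (a) only, and correct the SAP's reference to study medication. Keep the all-event table.
4. **Protect events already recorded.** Keep the investigator's original call and list it beside any reassigned category. Make the reassignment without knowledge of which set was worn, where the event description allows. The Medical Monitor already reviews events, but relabelling by the sponsor's own monitor in an open trial would otherwise add the discretion this change is meant to remove.

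The cost is wording in the protocol, SAP and event form, plus review of what should be a small number of events. The downside is that fewer events will be labelled device-related; the retained all-event table and the side-by-side listing keep that visible.

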8.3.4 TIME PERIOD AND FREQUENCY OF ADVERSE EVENT ASSESSMENT

Adverse event assessment and reporting shall occur continuously throughout the study. In the case of home use events, participants will be instructed to document issues in the provided Patient Diary and notify their respective study center per written instructions. Adverse events will be reviewed by a Medical Monitor as outlined in 10.1.6 – Safety Oversight.

8.3.5 ADVERSE EVENT REPORTING

A complication, adverse event (AE), serious adverse event (SAE) or Unanticipated Adverse Device effect (UADE) may become known to study personnel during study visits, participant interviews or during a study monitoring visit.

All adverse events (including UADEs and SAES) as well as local and systemic reactions shall be captured on the appropriate case report form (CRF). Data must include an event description, event start time, severity assessment, relationship to study product, resolution or event stabilization time/date.

NOTE: Co-morbidity and medical conditions present at baseline shall be considered pre-existing conditions and will not be reported as an adverse event. However, if a participant's condition deteriorates at any time during the study and requires medical intervention to resolve, this shall be captured as a study adverse event.

All adverse events and complications, regardless of relationship, severity or seriousness shall be fully documented and recorded.

